In the medical literature, the term UTI has been used when bacteriuria (presence of bacteria in the urine - with or without symptoms) is present. However, for individuals living with a SCI, this classification is not appropriate as the use of urinary catheters results in colonization of the bladder with bacteria (27). Differentiating between asymptomatic bacterial colonization and a true clinical infection can also be difficult to diagnose in persons with SCI since signs and symptoms in these individuals are often subtle and not always recognized as being related to a UTI. Diagnosis has been further challenged by a lack of consensus regarding what constitutes UTI symptoms, what combination of symptoms and laboratory findings are necessary for the diagnosis, and what symptoms require antibiotic treatment (vs being managed with alternative conservative measures, such as increasing fluid intake or catheterizations) (27). Thus, the National Institute on Disability and Rehabilitation Research (NIDRR) consensus conference and the International Clinical Practice Guidelines from the Infectious Diseases Society of America (IDSA)(28) have recommended criteria for the diagnosis of significant bacteriuria in persons with SCI and catheterassociated UTI (CA-UTI), respectively.

NIDRR Guidelines: (1) $\geq 10^2$ cfu/mL (colony forming units per milliliter) for catheter specimens from individuals on intermittent catheterization; (2) $\geq 10^4$ cfu/mL for clean-void specimens from catheter-free males using condom collection devices; and (3) any detectable concentration of uropathogens from indwelling catheters or suprapubic aspirates (29). Furthermore, investigators and clinicians have categorized UTIs as being asymptomatic or symptomatic.

An asymptomatic UTI is not considered a true infection, but rather colonization of the bladder with organisms and defined by the following criteria (30):

- No symptoms and
- Initial counts of 10² cfu/ml or higher (except for indwelling catheters)
- For individuals with indwelling catheters, any detectable bacteria

A symptomatic UTI in those having neurogenic bladder is defined as (31, 32):

- Increased bacterial urine colony counts,
- Increased white blood cells in the urine (pyuria), and

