- New onset of symptoms [cloudy, malodorous urine, discomfort or pain over the bladder or kidney areas, dysuria (painful or difficult urination), malaise, fever, lethargy or general feeling of un-wellness, increased incontinence, or symptoms specific to the population with SCI such as increased spasticity or autonomic dysreflexia].

IDSA Guidelines: Methods of Diagnosing Catheter Associated Asymptomatic Bacteriuria (CA-ASB) and CA-UTI

- (1) CA-UTI in patients with indwelling urethral, indwelling suprapubic, or intermittent catheterization is defined by the presence of symptoms or signs compatible with UTI with no other identified source of infection along with ≥10³ cfu/mL of ≥1 bacterial species in a single catheter urine specimen or in a midstream voided urine specimen from a patient whose urethral, suprapubic, or condom catheter has been removed within the previous 48 hours;
- (2) CA-ASB should not be screened for except in research studies evaluating interventions designed to reduce the incidence of CA-ASB or CA-UTI and in selected clinical situations, such as in pregnant women. CA-ASB in patients with indwelling urethral, indwelling suprapubic, or intermittent catheterization is defined by the presence of ≥10⁵ cfu/mL of ≥1 bacterial species in a single catheter urine specimen in a patient without symptoms compatible with UTI. CA-ASB in a man with a condom catheter is defined by the presence of ≥10⁵ cfu/mL of ≥1 bacterial species in a single urine specimen from a freshly applied condom catheter in a patient without symptoms compatible with UTI;

- (3) Signs and symptoms compatible with CA-UTI include new onset or worsening of fever, rigors, altered mental status, malaise, or lethargy with no other identified cause; flank pain; costovertebral angle tenderness; acute hematuria; pelvic discomfort; and in those whose catheters have been removed, dysuria, urgent or frequent urination, or suprapubic pain or tenderness. In patients with spinal cord injury, increased spasticity, autonomic dysreflexia, or sense of unease are also compatible with CA-UTI.
- (4) In the catheterized patient, pyuria is not diagnostic of CA-bacteriuria or CA-UTI. The
 presence, absence, or degree of pyuria should not be used to differentiate CA-ASB from CAUTI. Pyuria accompanying CA-ASB should not be interpreted as an indication for antimicrobial
 treatment. The absence of pyuria in a symptomatic patient suggests a diagnosis other than CAUTI (A-III);

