Urine collected for cultures will be collected as a clean-catch midstream technique from an immediately installed urine catheter or as a suprapubic aspiration from an installed catheter (52). For participants having a suprapubic catheter, the catheter will be clamped for 20 to 30 minutes until at least 5 mL of urine can be collected. The catheter will then be unclamped, and urine will be allowed to flow into a sterile plastic container. In those that use intermittent catheterization, participants will be required to first cleanse the urethral area with a castile soap towelette. A sterile 12 French straight catheter is inserted through the urethra into the bladder. The first portion of the urine stream should flow into the toilet in order to reduce the opportunities for contaminants to enter into the urine stream. The urine midstream is then collected into a clean container (any excess urine will be emptied into the toilet), Urine samples will be placed in

sterile storage vials and stored at 4C for less than 3 hours and sent to the Outpatient Care Center, Jewish Hospital for analysis. Symptomatic UTIs will be defined as a participant complaint of symptoms consistent with UTI (cloudy/foul smelling urine, fever, chills, increase in bladder and/or lower extremity spasms, worsening dysreflexia, leakage, or pain) combined with a positive leucocyte esterase and/or nitrates on dipstick urinalysis or a urine microscopy with > 10 WBC/HPF (white blood cells/high powered field) with a urine culture with >10⁵ bacteria/ml (46). Note that urine smell and cloudiness alone (i.e. without other symptoms) are not considered UTI signs, given their high prevalence in this catheterizing population. All cultured microorganisms will be identified to the species level and quantified as colony-forming units per ml (cfu/ml⁻¹) (16). If the microorganism(s) cultured is/are resistant to three or more different antimicrobial agents to which the microorganism would normally be susceptible, it will be defined as being multi-resistant. If a participant is diagnosed having a symptomatic UTI necessitating systemic antibiotics by the study physician/nurse practitioner, he/she will follow standard of care treatment under provider oversight. The study physician/nurse practitioner will recommend whether or not continuation of either the instillation or clamping protocol is appropriate for the participant during systemic antibiotic treatment.

5. Blood Draw

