- An unusual decrease in the amount of urine while using gentamicin injection (pediatric)

Gentamicin may also be applied topically or instilled locally into the bladder, as described in the intervention for this study. Risks for the gentamicin intervention in this study include those associated with the local application in the bladder.

Risks of Gentamicin bladder instillation and associated assessments:

Likely

- Feelings of shyness
- Significant changes in heart rate and/or blood pressure from bladder clamping or urodynamics
- Autonomic dysreflexia symptoms (sudden high blood pressure) that resolves when the cause is removed (*individuals with an injury level above T6 and in those who have previously experienced these symptoms)
- Discomfort and/or skin irritation at the site of needle insertion for the blood draw

• Skin irritation from adhesive tape and/or pads

Less Likely

- Bleeding, bruising and/or pain from blood draw
- Lightheaded during the blood draw
- Mild discomfort, especially during urination after assessments of the bladder
- Urinary tract infection requiring oral antibiotics after urodynamics
- Discomfort from lying still for ultrasound
- Antibiotic-related vaginal yeast infection and/or diarrhea (opportunistic infection) from gentamicin instillation
- Localized allergic reaction to gentamicin (rash, redness, swelling around groin region)

Rare

- Infection from blood draw
- Autonomic dysreflexia symptoms (sudden high blood pressure) but the cause cannot be identified, and the high blood pressure does not resolve, and medical intervention is required (*individuals with an injury level above T6 and in those who have previously experienced these symptoms)
- Urinary tract infection requiring intravenous antibiotics
- Growth of organisms resistant to gentamicin
- Intravesical (bladder) absorption of gentamicin
- Excessive pain, fever, chills

E. Adequacy of Protection against Risk

1. Recruitment and Informed Consent

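### The symptomatic-UTI definition has no timing or alternative-cause rule, so dysreflexia (and possibly spasm) provoked by a dwell or clamping can be counted as an infection

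*Combined protocol and SAP*

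**What the plan says.** The operative definition is in Research Procedures, item 4 (Urine Sample Collection and Culture), and is attributed to reference 46. It has three parts:

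- **Symptom:** a participant complaint from a list that includes "increase in bladder and/or lower extremity spasms, worsening dysreflexia, leakage, or pain".
- **Urinalysis:** "combined with a positive leucocyte esterase and/or nitrates on dipstick urinalysis", or more than 10 white cells per high-powered field on microscopy.
- **Culture:** "with a urine culture with" more than 10⁵ bacteria/ml. I read the culture as required in every case, which is the reading more favourable to the plan.

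The only exclusion is that "urine smell and cloudiness alone (i.e. without other symptoms) are not considered UTI signs".

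The background (section I.D) cites conditions that the operative definition does not repeat. One source asks for "New onset of symptoms". The other defines catheter-associated UTI by the "presence of symptoms or signs compatible with UTI with no other identified source of infection". The same section says that "the use of urinary catheters results in colonization of the bladder with bacteria".

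The protocol also treats dysreflexia as an effect of the procedures. Section I.A ties it to bladder distention in injuries at T6 and above. Research Procedures, items 1 and 2, have the bladder drained at once if it occurs and set the retention time by it. Section III.D.1 lists dysreflexia that goes away once its trigger is removed as Likely in at-risk participants, along with "Significant changes in heart rate and/or blood pressure from bladder clamping or urodynamics".

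**The concern.** Dysreflexia is both a qualifying UTI symptom and an expected effect of filling or clamping the bladder. The definition gives no way to tell the two apart. A participant who becomes dysreflexic during a dwell, and whose urine is colonised and pyuric, meets it without having an infection.

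Symptomatic UTI is the outcome behind Hypothesis 1.1 and the sample size. With 12 participants per arm, a few such episodes could matter. Exposure to the provoking procedure is set by arm and catheter type, so the error need not be equal across groups. The no-instillation arm is also unblinded (Blinding Plan), and every episode starts with a participant's complaint.

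**Working it through.** **The plan's own figures.** Inputs from the Statistical Plan: 12 per arm; reduction of 2 (SD 1.7) with gentamicin and 0 (SD 0) without instillation; two-sided 0.05.

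- Two-sample, unequal variance: noncentrality = 2/√(1.7²/12 + 0²/12) = 2/0.491 = 4.08, df 11; power 95.9% (stated 96%).
- Paired, change of 1.5: 1.5/0.491 = 3.06, df 11; power 79.4% (stated 80%).
- Paired, change of 2: noncentrality 4.08, df 11; power 95.9% (stated 97%).

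These reproduce to within about one point. Nothing below corrects them.

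**How well do the laboratory criteria filter?** Section I.D says catheter use leads to colonisation. It defines asymptomatic bacteriuria at 10⁵ cfu/mL or more, essentially the trial's culture cut-off, and says pyuria should not be used to separate it from infection. Most of the separation therefore falls to the symptom criterion.

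**Is there a hidden timing rule?** The words increase and worsening imply change, but no reference period is given. Symptom duration is collected on the UTI data set (item 8), but no counting rule uses it.

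**Exposure over 80 days** (section II.B; items 1 to 3; Figure 2):

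- Gentamicin and saline: 2 × 80 = 160 dwells each, with the same retention-time training.
- No instillation, suprapubic: 4 × 80 = 320 clampings under item 3. If clamping only matches the two daily instillations, as Figure 2 may be read, 2 × 80 = 160.
- No instillation, intermittent catheterization: 0.
- Mean of the no-instillation arm with the 6/6 split: (6 × 320 + 6 × 0)/12 = 160, or (6 × 160 + 6 × 0)/12 = 80.

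**Illustration on assumed values (none is in the documents).** Assume 0.25 to 1 procedure-provoked complaint per instillation participant, proportional to exposure in the other groups. Spurious UTIs per participant = complaints × probability that the laboratory criteria are met. Bias = control minus gentamicin; a positive value favours gentamicin.

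| Laboratory criteria met | Gentamicin | Saline | Bias vs saline | Bias vs none, 4 clampings/day | Bias vs none, 2 clampings/day |
|---|---|---|---|---|---|
| (a) 80% in all arms | 0.2 to 0.8 | 0.2 to 0.8 | 0 | 0 | −0.1 to −0.4 |
| (b) 30% gentamicin, 80% controls | 0.075 to 0.3 | 0.2 to 0.8 | 0.125 to 0.5 | 0.125 to 0.5 | 0.025 to 0.1 |

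The zero in row (a) at four clampings a day is an average of opposite errors. Suprapubic controls would have 0.4 to 1.6 spurious UTIs (bias +0.2 to +0.8) and intermittent-catheterization controls none (bias −0.2 to −0.8).

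With no true effect and SD 1.7 in both arms, a bias of 0.5 gives noncentrality 0.5/(1.7 × √(2/12)) = 0.72, df 22. Two-sided rejection is then 10.6% instead of 5%; at a bias of 0.25 it is 6.4%. In row (a), adding Poisson variance to the plan's own SDs takes the 96% power to 94% to 83% (four clampings) or 92% to 71% (two). These figures show what the assumptions imply. They are not estimates for this trial.

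**The case against.** The case for leaving the definition alone has real substance.

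- **The procedure is titrated to avoid dysreflexia.** Retention time is lengthened only after three stable days, and home use follows stable laboratory sessions. This stands, and should make such events less frequent. It does not say how a remaining event is classified.
- **Much of the information is already collected.** Blood pressure tolerability is a separate outcome in Specific Aim 1, home blood pressure is recorded during instillations, and symptom duration is on the UTI form. This also stands; the missing piece is a rule. Home monitoring is specified for at least 15 minutes, whereas a dwell may last 2 hours.
- **The background wording would not solve the problem by itself.** The phrase about no other source concerns another infection, so copying it would not exclude dwell-related dysreflexia. Correct, which is why the fix names the cause and the timing of the symptom.
- **The definition comes from reference 46, the source of the planned effect and SD.** Changing it weakens that link, and a true infection may first show as dysreflexia during filling. Both points stand and are met by a sensitivity analysis.

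A reader might also infer that dwell and clamping are expected to cause all four listed symptoms. The available text does not support that. Spasm and leakage are not in the risk list as effects of dwell or clamping. Spasm has only indirect support, from involuntary contractions during urodynamic filling. Pain appears only as mild discomfort after assessments (Less Likely) or excessive pain (Rare). Nor are the laboratory criteria worthless: the documents do not say that colonised participants routinely exceed 10⁵/ml and have a positive urinalysis.

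**Conclusion.** The point holds for dysreflexia and, less firmly, for spasm: the definition as written can count a procedure effect as a UTI when the urine is colonised and pyuric. Exposure to that risk differs by arm and catheter type.

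Two stronger readings should be resisted.

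- **A share of spurious UTIs.** One might take the Likely band (more than 30%) and compute 0.30 × 12 = 3.6 participants per arm. That denominator is wrong. The risk entry is limited to injury above T6 or previous dysreflexia, injury level is not an entry criterion, and the list also covers urodynamics and other assessments. With no misclassification rate in the documents, no percentage inflation can be stated.
- **A fixed direction.** One might conclude that the error favours gentamicin. Gentamicin and saline share a blinded procedure, so bias between them needs gentamicin to suppress the laboratory criteria. That is plausible, but its size is unknown. Against no instillation, the contrast used for power, the sign changes with clamping frequency and laboratory positivity.

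The stated power is not disproved. The definition should be amended before data collection, because timing that is not recorded prospectively may not be recoverable.

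**What to change.** For endpoint counting only, with no bearing on treatment:

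1. Require the qualifying symptom to be new or worse than the participant's pre-intervention state, with no other identified cause.
2. Add a tick-box to the UTI form for whether dysreflexia or spasm occurred only during a dwell or clamp period. Report such events as tolerability outcomes.
3. In the main analysis, do not count an episode whose only qualifying symptom was dysreflexia or spasm confined to those periods.
4. Run a sensitivity analysis on the reference 46 definition as now written, counting those episodes.
5. Reconcile the clamping frequency between Research Procedures, item 3 (four times a day) and Figure 2 (clamping for the duration of instillation), since exposure in the control arm depends on it.

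The cost is a short addition to the definition, one tick-box and one extra analysis. A few borderline or true episodes may drop out of the main count, and comparability with the study behind the planned effect is slightly reduced. The sensitivity analysis covers both.

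### Symptomatic UTI may require a culture above 10⁵/ml, so part of any fall under gentamicin could be symptomatic episodes moving into the 10³ to 10⁵ band; add a prespecified count at ≥10³

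*Combined protocol and SAP*

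**What the plan says.** Under Urine Sample Collection and Culture, a symptomatic UTI needs a complaint of compatible symptoms, then a "positive leucocyte esterase and/or nitrates on dipstick urinalysis or a urine microscopy with > 10 WBC/HPF", then the phrase "with a urine culture with >10⁵ bacteria/ml". The definition cites the earlier gentamicin instillation study, which also supplies the effect size in the Statistical Plan. The same section states: "All cultured microorganisms will be identified to the species level and quantified as colony-forming units per ml".

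Section I.D gives two sets of published criteria as background:

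- **IDSA, symptomatic catheter-associated UTI** (indwelling urethral, suprapubic or intermittent catheter): compatible symptoms or signs with no other source of infection, "along with ≥10³ cfu/mL of ≥1 bacterial species in a single catheter urine specimen".
- **IDSA, asymptomatic bacteriuria:** "≥10⁵ cfu/mL of ≥1 bacterial species in a single catheter urine specimen in a patient without symptoms".
- **NIDRR, significant bacteriuria:** ≥10² cfu/mL "for catheter specimens from individuals on intermittent catheterization", and "any detectable concentration of uropathogens from indwelling catheters or suprapubic aspirates". The accompanying definition of symptomatic UTI asks for increased colony counts, pyuria and new symptoms, with no numerical cut-off.

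Symptomatic UTI is the first outcome in Hypothesis 1.1 and the only outcome in the power statement. Apart from the citation, the plan gives no reason for 10⁵ and no analysis at a lower cut-off.

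**The concern.** A strict culture cut-off unrelated to treatment would mainly cost sensitivity, about equally in each arm. Here the treatment acts on the marker that is being cut. The background describes high local concentrations of a bactericidal drug, bacteriuria is itself an Aim 1 outcome, and people colonised with gentamicin-resistant bacteria at baseline are excluded.

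Consider two participants with the same fever, spasms and pyuria on microscopy. Where the culture clause applies, the one growing 2 × 10⁵ per ml is counted and the one growing 5 × 10⁴ is not, although both exceed the IDSA level for symptomatic catheter-associated UTI. If gentamicin moves episodes from the first state to the second, the count falls while people are just as ill. Blinding does not prevent this, because the shift is in the laboratory value. The within-arm pre-post comparison is exposed too, since the later measurement is taken on drug.

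At stake is what a positive result may be called: fewer symptomatic infections, or fewer symptomatic episodes with a high colony count.

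**Working it through.** **1. The plan's own figures.** The documents give no figure for the effect of the cut-off. The stated powers (n = 12, SD 1.7, two-sided 0.05, noncentral t on 11 df) reproduce closely:

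- Paired, mean change 1.5: noncentrality 1.5 ÷ (1.7/√12) = 3.06, power 79.4% (stated 80%).
- Paired, mean change 2: noncentrality 2 ÷ (1.7/√12) = 4.08, power 95.9% (stated 97%).
- Gentamicin against no instillation, SDs 1.7 and 0: the same noncentrality and df, power 95.9% (stated 96%).

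None of these uses the culture cut-off, so this point changes no stated figure.

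**2. Distance between cut-offs.** 10⁵ ÷ 10³ = 100. The trial's culture level is 100 times the IDSA level for symptomatic patients.

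**3. Illustration of the shift.** All inputs here are assumptions. In symptomatic episodes that meet the dipstick or microscopy criterion, log10 cfu/ml is normal with mean m and SD 1 in controls. Gentamicin lowers it by L, and the number of such episodes is the same in both arms. Culture is required for every episode.

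Proportion counted at cut-off c: control Φ(m − c), gentamicin Φ(m − L − c), with c = 5 or 3.
Apparent reduction = 1 − Φ(m − L − c) ÷ Φ(m − c).

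| m | L | Above 10⁵: control → gentamicin | Apparent reduction | At ≥10³: control → gentamicin | Apparent reduction |
|---|---|---|---|---|---|
| 5.5 | 1 | 0.691 → 0.309 | 55% | 0.994 → 0.933 | 6.1% |
| 6 | 1 | 0.841 → 0.500 | 41% | 0.999 → 0.977 | 2.1% |
| 7 | 1 | 0.977 → 0.841 | 14% | 1.000 → 0.999 | 0.1% |
| 6 | 0.5 | 0.841 → 0.691 | 18% | 0.999 → 0.994 | 0.5% |
| 7 | 0.5 | 0.977 → 0.933 | 4.5% | 1.000 → 1.000 | under 0.1% |

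The missing episodes appear in the intermediate band. At m = 6 and L = 1, the share between 10³ and 10⁵ is 0.999 − 0.841 = 0.157 in controls (from unrounded values) and 0.977 − 0.500 = 0.477 under gentamicin.

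**4. Scale against the planned effect.** Assume also 3 true episodes per person in six months, with m = 6. The spurious extra reduction at 10⁵ is 3 × (0.841 − 0.691) = 0.45 UTIs for a 0.5 log fall and 3 × (0.841 − 0.500) = 1.02 for 1 log. At ≥10³ it is 0.01 and 0.06. The Statistical Plan expects a drop of at least 2. In simulation (Poisson counts, 12 against 12, Welch test on change, no true difference in episodes), the chance of a significant result at 10⁵ was about 8% for 0.5 log and 20% for 1 log, against about 5% for both at ≥10³.

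**5. Would agreement in direction be a safeguard?** No. The counts are nested and tend to move together. In the same null setting at m = 6, with a 0.5 or 1 log fall, at least about 85% of the spuriously significant 10⁵ results also favoured gentamicin at ≥10³.

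**The case against.** Five points on the other side carry weight.

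- **The cut-off is sourced.** It comes from the study behind the effect size, and section I.D is background that itself reports a lack of consensus on diagnostic criteria. A reader might infer that the endpoint contradicts the protocol's guidelines, or that 10⁵ is simply the level for asymptomatic patients. The documents do not support that. The IDSA text pairs 10⁵ with absence of symptoms, but the other criteria put asymptomatic colonisation at 10² or any detectable bacteria.
- **The culture clause may bind only the microscopy branch.** On that reading, symptoms with a positive dipstick count without culture, and the bias is smaller. This stands, and the point is conditional on it.
- **The lower cut-off is less specific.** Catheterised bladders are colonised, so ≥10³ may discriminate little. The IDSA definition also excludes other sources of infection and does not use pyuria to separate infection from colonisation. This is why ≥10³ should be a sensitivity count and not a replacement.
- **A fall in bacteria may itself relieve symptoms.** Nothing in the documents shows that it does not. If it does, symptomatic episodes will also fall at ≥10³ and regardless of culture, and the added counts will show it.
- **Cross-checks exist.** Hypothesis 1.1 also names oral antibiotic courses, and the International SCI UTI data set records symptoms, dipstick and culture for possible UTIs. These help only in part, because no analysis of episodes below the cut-off is prespecified.

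**Conclusion.** The point holds as a limited one. Where culture is required, the trial's count cannot separate fewer symptomatic infections from equally symptomatic episodes with lower colony counts, and any such shift would favour gentamicin. Under the assumptions shown (normal log10 counts, SD 1, a 1 log fall, no symptom benefit), the apparent reduction at 10⁵ runs from about 14% to 55% for control means of 7 down to 5.5, against about 0.1% to 6% at ≥10³. The documents give no mean, SD or log fall, so this is a range of possibilities and not an estimate. A reader might go further and infer that a positive trial would be an artefact. That does not follow, because it needs both a sizeable fall in counts during symptomatic episodes and no effect on symptoms, and the documents establish neither. This is a cheap improvement, not a flaw that invalidates the endpoint.

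**What to change.** 1. Keep the present definition for comparability with the cited study, and state whether the culture clause applies to both the dipstick and the microscopy branch.
2. Prespecify a sensitivity analysis counting symptomatic episodes that meet the same dipstick or microscopy criterion at ≥10³ cfu/mL of at least one species. Report the between-arm difference with its confidence interval.
3. Report by arm the symptomatic episodes with counts from 10³ to 10⁵, and the symptomatic episodes regardless of culture.
4. State the interpretation in advance. If the ≥10³ estimate is materially smaller than the 10⁵ estimate, or the intermediate band is larger under gentamicin, describe the result as fewer high-count episodes and not as fewer symptomatic infections. Fix what counts as materially smaller before unblinding. Do not rely on both estimates merely favouring gentamicin, since step 5 of the working shows how weak that safeguard is.

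**Cost:** definition wording and extra tabulations from cultures already quantified and forms already collected, with no added visits, specimens or participants. With 12 per arm the added estimates will be imprecise. The lower cut-off is less specific in colonised bladders. These are counting rules for analysis only and do not bear on who is treated.
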